### 3.4 Randomization and blinding

Eligible Patient will be randomized in a 2:1 fashion to either ladarixin or placebo.

Randomization will be performed through IRS. Each Patient Kit number will be randomly associated with a treatment group. The randomization list will be provided to the facility responsible for IMP packaging/labelling for the purpose of IMP preparation. Each randomized patient will be allocated with randomization number according to the stratified randomization list. Dropouts after randomization will not be replaced.

Randomization will be stratified by site to ensure balanced assignment across treatment groups. The stratified permuted block randomization list will be generated with a computer procedure by an independent statistician not involved in the conduct of the study. A master randomization list will be generated, with patients balanced between sites in accordance to randomization ratio (2:1).

Access to individual patient treatment code will be allowed only in the event of a medical emergency where the knowledge of patient treatment is required to provide the patient with appropriate care. The investigator will be provided with a protected access to the randomization system to allow opening of the treatment allocation for a specific patient in case of a medical emergency.

# PPD

Dompé Pharmacovigilance contact person will be provided also with envelopes of the randomization number code break (to reveal the planned treatment arm assigned at the Randomization Visit) in order to unblind a specific patient for safety reporting. Unblinding events will be recorded and reported in the final study report.

The randomization code will be broken according to study procedures after the last enrolled patient has completed his/her follow-up visit at 12 months.

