### Study design

The study will be a phase 2, multicenter, double-blind, placebo-controlled study. It will randomize approximately 75 adult patients with new-onset type 1 diabetes (T1D) and preserved  $\beta$ -cell function (fasting C-peptide  $\geq 0.205$  nmol/l) at baseline. Patients will be assigned (2:1) to receive either oral ladarixin treatment (400 mg b.i.d. for 13 cycles of 14 days on/14 days off - treatment group) or placebo (control group). Recruitment will be competitive among the study sites, until the planned number of patients is randomized.

Ladarixin and placebo will be both administered for 1 year. All patients will be followed-up for 18 months from the 1st administration of the study medication. The study database will be locked and data analyzed when the last patient randomized has completed month 12 follow-up visit. After this time point, the follow-up will continue under open-label conditions up to month 18.

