#### 6.1.4. Blinding

Appearance, including packaging and labelling, of the IMP (capsules, packaging) will not allow to recognize actual treatment (either ladarixin or placebo).

During the trial, blinding will be broken by the Investigator for emergency purposes only, where knowledge of the blinded treatment could influence further patient care. In addition, safety reports will be unblinded, as per regulatory requirements.

Study blind will be broken after database lock.

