# PPD

dose. The study will proceed under double-blind condition up to the month 12 visit of the last patient randomized. Thereafter, the blind will be broken and remaining follow-up will proceed in an open fashion. This approach will allow to anticipate access to safety and efficacy data without significantly affecting data integrity.

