## 3.5 Overview of planned statistical analyses

The study was originally planned to perform the following statistical analyses:

- Final analysis: to be conducted when all enrolled subjects have completed the Month 12 follow-up visits, and the study database has been locked.
- Addendum at Final analysis: to be conducted when all enrolled subjects have completed the open phase study post unblinding up to Month 18.

Considering the premature closure of the study, a unique analysis will be performed when all enrolled subjects have completed all the follow-up visits and the study database has been locked.

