## 4.8 Changes in the planned analysis

Due to the company decision to stop the enrolment, fewer patients compared to the originally planned will be available for the analysis. Thus, the following changes were implemented:

- one single final analysis is planned after DB lock;

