## 4.9 Blind Data Review Meeting

A Blind Data Review Meeting (BDRM) will be held before the database lock and unblinding of the data. Any other details will be provided in the BDRM Report.

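### SAP v3.0 moves the only lock and analysis to the end of follow-up but keeps the Month 12 code break, so its blinding, data review and lock rules cannot all be followed

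*SAP*

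**What the plan says.** **Protocol.** The blind, the lock and the analysis were tied to one milestone. Section 1 (Study design) says: "The study database will be locked and data analyzed when the last patient randomized has completed month 12 follow-up visit". Sections 3.3 and 9.2 break the code once the last patient has had the Month 12 visit. Section 9.3 places the final analysis there, with an addendum after Month 18. Section 6.1.4 sets the order: "Study blind will be broken after database lock".

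**SAP v3.0, lock and analysis.** Section 3.5 presents the Month 12 analysis as the earlier plan, "to be conducted when all enrolled subjects have completed the Month 12 follow-up visits, and the study database has been locked", and puts in its place "a unique analysis will be performed when all enrolled subjects have completed all the follow-up visits and the study database has been locked". Section 4.8 repeats this: "one single final analysis is planned after DB lock".

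**SAP v3.0, code break.** Section 3.1 keeps double-blind conditions up to the Month 12 visit of the last randomized patient and continues: "Thereafter, the blind will be broken and remaining follow-up will proceed in an open fashion". Section 3.4 gives the same timing: "The randomization code will be broken according to study procedures after the last enrolled patient has completed his/her follow-up visit at 12 months".

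**SAP v3.0, blind review.** Section 4.9 says the Blind Data Review Meeting "will be held before the database lock and unblinding of the data". Section 5.2 has protocol violations settled at that meeting while the treatment code is still closed.

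**The concern.** The Month 12 code break was safe in the protocol because the Month 12 data were to be locked at the same milestone. SAP v3.0 takes that lock away and leaves the code break where it was. Followed literally, the treatment code opens while the primary endpoint data can still be changed, and the blind review of the final data cannot be blind.

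What is exposed is the handling of data already collected:

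- Under protocol 11.3, investigators answer queries and sign the eCRF before lock. Under Appendix 14.3.1, sites themselves enter central laboratory results.
- Severe hypoglycaemia after baseline comes from patient diaries, and missing event dates are derived (SAP 9.1, Table 3).
- Violations are classified case by case (SAP 5.2).
- The choice between Chi-square and Fisher has no stated criterion (SAP 7.1), and post-hoc analyses may be added in the light of results (SAP 4.1).

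A second question is whether the v3.0 changes were themselves made blind. They drop the logistic regression and multiple imputation, and they revise the severe hypoglycaemia derivation and the compliance rules. The recurrent-event model now uses model-based variance (SAP 7.2.1.8 and 12.2), where protocol 9.5.2.2 named a robust sandwich estimate.

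**Working it through.** There is no stated figure to reproduce. The check concerns the order of events, then the length of the interval.

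**1. Order of events**

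| Event | Timing in the documents |
|---|---|
| Code break | After the last patient's Month 12 visit (SAP 3.1, 3.4) |
| Remaining follow-up | Open, to Month 18 (SAP 3.1) |
| Data review and violation calls | Before unblinding (SAP 4.9, 5.2); the review also before lock (4.9) |
| Lock and only analysis | After all follow-up visits (SAP 3.5, 4.8) |
| Breaking of the blind | After lock (protocol 6.1.4) |

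There are two ways to place the review:

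- Before a Month 12 code break, it is blind but cannot cover data from Month 12 to Month 18.
- Before the single lock, it covers everything but follows the code break.

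Neither meets all the rules. Protocol 6.1.4 fails in both cases, because the only lock comes after Month 18. A separate Month 12 data cut, or a team kept blinded, could remove the conflict, but the SAP names neither.

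**2. Interval from code break to last visit**

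Inputs are the visit windows in SAP 3.2: Month 12 = week 52 ± 2, Month 18 = week 78 ± 2.

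- Nominal: 78 − 52 = 26 weeks.
- Shortest: 76 − 54 = 22 weeks.
- Longest: 80 − 50 = 30 weeks.

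Time for cleaning between the last visit and lock is extra and is not given. If the code break followed the single lock, the interval would be 0.

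**3. Position relative to SAP v3.0**

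Inputs are the enrolment-stop communication of 28 March 2022 (SAP section 1), the run-in limit of 100 days (protocol 3.3) and the v3.0 date of 7 May 2024 (SAP Revision History). The date of last randomization is not given, so two assumptions are shown for the last first dose.

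| | A: 28 Mar 2022 | B: 28 Mar 2022 + 100 days = 6 Jul 2022 |
|---|---|---|
| Month 12, nominal (+364 days) | 27 Mar 2023 | 5 Jul 2023 |
| Month 12, latest (+378 days) | 10 Apr 2023 | 19 Jul 2023 |
| Month 18, nominal (+546 days) | 25 Sep 2023 | 3 Jan 2024 |
| Month 18, latest (+560 days) | 9 Oct 2023 | 17 Jan 2024 |
| Nominal Month 12 to v3.0 | 407 days = 58.1 weeks | 307 days = 43.9 weeks |
| Latest Month 12 to v3.0 | 393 days = 56.1 weeks | 293 days = 41.9 weeks |

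The trigger therefore falls about 42 to 58 weeks before v3.0. A Month 12 visit at week 50 under A would stretch this to 60 weeks. For the trigger to come after v3.0 even with a Month 12 visit at week 54, the last first dose would have to be later than 7 May 2024 − 378 days = 25 April 2023, which is 393 days after the stop communication.

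**The case against.** **The word *after* in SAP 3.4 may set only an earliest point.** A code break following the single lock would then satisfy 3.4, 3.5, 4.9, 5.2 and protocol 6.1.4 together. This is a fair reading of 3.4 alone, but it does not rescue 3.1, which opens the blind and makes the remaining follow-up open from Month 12.

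**Section 3.1 may be uncorrected design text.** It still describes 75 patients and recruitment to the planned number, although enrolment was stopped. That may be how the conflict arose. But where v3.0 keeps superseded content in 3.3 and 3.5 it says so, and 3.1 and 3.4 carry no such label.

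**Removal of the Month 12 lock is an inference.** No sentence cancels a Month 12 cut outright. The inference from 3.5 and 4.8 is clear, however, and no section keeps such a cut.

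**The route to bias is narrow.** Most of this stands. By the last patient's Month 12 visit, every Month 12 insulin dose has been recorded and every HbA1c sample taken, so the break cannot influence dosing that feeds the primary endpoint. Violation calls remove nobody from the FAS, which is everyone randomized and dosed. The composite of HbA1c and no severe hypoglycaemia counts events only to Month 12. Open follow-up from Month 12 to Month 18 is the protocol's own design, so open Month 18 assessment is not a consequence of v3.0. The stated reason for the v3.0 changes, fewer patients, needs no knowledge of treatment, and v3.0 disclaims formal hypothesis testing. Between-arm tests do remain, and significant p-values are to be placed on the figures.

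**Conclusion.** The inconsistency is real and should be corrected. Sections 3.1 and 3.4 were not brought into line when 3.5 and 4.8 moved to one late lock. As written, the Month 12 primary data stay editable for about 26 weeks after the code break (22 to 30 with windows), plus cleaning time, and a blind review of the final data is not possible. Those intervals rest only on the visit windows and on reading 3.1 literally.

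The consequence is limited to queries, diary-based derivations, violation calls and analysis choices, in an analysis that claims no confirmatory result.

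A reader might infer that the code was in fact opened at Month 12 and that v3.0 was written unblinded. The documents do not support this: they show a trigger, not an event, and protocol 6.1.4 points the other way. The gap of 42 to 58 weeks depends on a last first dose between 28 March and 6 July 2022, which is an assumption. It shows only that the question needs an answer, and v3.0 gives none.

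**What to change.** Reconcile SAP 3.1 and 3.4 with SAP 3.5, 4.8, 4.9 and 5.2, and with protocol sections 1, 3.3 and 9.2, which also prescribe the Month 12 break. Two routes are consistent:

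1. Keep the code closed to sponsor, data management and statistics until the single lock, with the blind review before it.
2. If the code was opened at Month 12, document a cleaned and locked Month 12 data cut, with the blind review completed before the break.

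In either case, state the actual code-break date, who had access, and whether the v3.0 analysis changes were made before or after unblinding. If the code was opened without a locked cut, say so in the SAP and the clinical study report, and label the later decisions accordingly.

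The cost is wording in the SAP, matching reconciliation of the protocol and, if the code is still closed, an instruction to the randomization system. No patients and no further analysis are needed. Under the assumptions above, the last Month 18 visit fell by 9 October 2023 (A) or 17 January 2024 (B), about 30 or 16 weeks before v3.0 (211 and 111 days), so the remedy may be mainly a record of what was done.

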## 3.5 Overview of planned statistical analyses

The study was originally planned to perform the following statistical analyses:

- Final analysis: to be conducted when all enrolled subjects have completed the Month 12 follow-up visits, and the study database has been locked.
- Addendum at Final analysis: to be conducted when all enrolled subjects have completed the open phase study post unblinding up to Month 18.

Considering the premature closure of the study, a unique analysis will be performed when all enrolled subjects have completed all the follow-up visits and the study database has been locked.

## 3.6 Efficacy endpoints

### 3.6.1 Primary endpoint

The primary efficacy endpoint is the proportion of patients with HbA1c <7% and daily insulin requirement <0.50 IU/Kg/day at Month 12.

### 3.6.2 Secondary efficacy endpoints

The secondary efficacy endpoints are the following:

- Proportion of patients with HbA1c <7% and daily insulin requirement <0.50 IU/Kg/day at Month 6 and 18;
- Proportion of patients with a reduction in HbA1c > 0.5% from baseline and daily insulin requirement <0.50 IU/Kg/day at Month 6, 12, and 18;
- 2-hour Area Under the Curve (AUC) of C-peptide response to the Mixed Meal Tolerance Test (MMTT) at Month 6, 12, and 18;
- Time in range (TIR) by Continuous Glucose Monitoring (CGM) at Month 6, 12, and 18;
- HbA1c levels at Month 6, 12, and 18;
- Proportion of patients with HbA1c <7% who did not experience severe hypoglycaemic events during treatment at Month 6, 12, and 18;
- Additional Glucose Variability Indices derived from CGM at Month 6, 12, and 18;
- Number of self-reported episodes of severe hypoglycaemia at Month 6, 12, and 18;
- Average (previous 3 days) daily insulin requirements (IU/kg/day) at Month 6, 12, and 18;
- Estimated Glucose Disposal Rate (eGDR) at Month 6, 12, and 18;

# PPD

CCI

## 3.7 Safety endpoints

The safety endpoints are the following:

- Adverse Events (AEs) and Serious Adverse Events (SAEs) throughout the study;
- Safety Laboratory Tests at Week 11, Week 23, Week 35, Month 12 and Month 18 (or withdrawal);
- Vital signs at Week 11, Week 23, Week 35, Month 12 and Month 18;

## 4. Statistical Analysis

### 4.1 General

Appropriate descriptive statistics will be produced, according to the variable. For continuous data n, mean, standard deviation (SD), median and range (minimum and maximum) will be presented. For categorical data, frequency distributions and percentages will be presented.

Unless otherwise specified, hypothesis testing will be carried out at the alpha = 0.050 level (one-sided) when comparing treatments. For all inferential analyses, p-value will be rounded to three decimal places. Statistical significance will be declared if the rounded one-sided p-value will be less than or equal to 0.050.

Additional post-hoc analysis may be produced to further allow comparison between ladaxirin and placebo, according to the results obtained. Any unplanned analyses as well as deviations from the original statistical plan will be clearly documented in the Clinical Study Report.

Derivation rules for efficacy and safety analyses are reported in Table 3 in section 9.

All the data collected and derived in the study will be presented in subject data listings.

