## 9. STATISTICAL ISSUES

### 9.1. SAMPLE SIZE

The sample size of the study is calculated on the “proportion of patients with a HbA1c <7% and daily insulin requirement <0.50 IU/Kg/day”, a post-hoc composite endpoint derived from data of the phase 2 trial [CC1], considering a larger effect size expected from the longer treatment length (one year versus 3 months).

Based on these assumptions, and considering a randomization ratio 2:1 (ladarixin:placebo) and a one-sided alpha of 0.05, seventy- five (75) patients randomized in the trial will allow to achieve a power of approximatively 80% to detect at least 35% of difference in terms of primary endpoint in favor of ladarixin vs placebo, assuming that the proportion of patients in the placebo group with a HbA1c <7% and daily insulin requirement <0.50 IU/Kg/day at 12 months will range between 45% and 55%.

The above sample size will take into account a drop-out rate of approximately 10%.

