## 9.5. STATISTICAL METHODOLOGY

All patient data collected on the eCRF will be listed by patient and center.

Appropriate descriptive statistics will be produced, according to the variable. For continuous data n, mean, standard deviation, median and range (minimum and maximum) will be presented. For categorical data, frequency distributions and percentages will be presented. If appropriate, confidence intervals around the mean or the proportions will be presented.

All AUC analyses will be based on actual rather than scheduled timings and will be calculated using the trapezoidal rule. In case of partial information collected during an assessment:

- if actual time is not recorded, the scheduled time will be used instead;
- missing values will be imputed via linear interpolation;
- when C-peptide values are below the limit of detection, the limit value will be assumed in the calculation of area under the curve.

The last available basal sample (time and value) will be used as the first sample in the computation of the AUC. If required, inferential statistics will be conducted on  $\log(x+1)$  transformed data, according to Lachin [2011].

Unless otherwise specified, the significance level used for statistical testing will be 0.05 and one-sided tests will be used.

A Statistical Analysis Plan will be issued with more technical and detailed elaboration of the principal features of statistical analyses. Additional post-hoc analysis may be produced to further allow comparison between ladarixin and placebo, according to the results obtained.

Any deviations from the original statistical plan (including unplanned analyses) will be clearly documented in the Clinical Study Report.

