### 9.5.2. Analysis of efficacy variables

#### 9.5.2.1. Primary analyses

The proportion of patients with  $\text{HbA1c} < 7\%$  and daily insulin requirement  $< 0.50 \text{ IU/Kg/day}$  at Month 12 (primary endpoint) will be analyzed by means of logistic regression possibly adjusting by pre-defined baseline factors that will be defined in the SAP.

The null hypothesis  $H_0$  is that the proportion of patients with a  $\text{HbA1c} < 7\%$  and daily insulin requirement  $< 0.50 \text{ IU/Kg/day}$  at Month 12 in ladarixin ( $\pi_{\text{LADARIXIN}}$ ) is lower or equal the placebo one ( $\pi_{\text{PLACEBO}}$ ):

$$H_0: \pi_{\text{LADARIXIN}} \leq \pi_{\text{PLACEBO}}$$

$$H_1: \pi_{\text{LADARIXIN}} > \pi_{\text{PLACEBO}}$$

The null hypothesis will be rejected, and superiority of ladarixin in terms of primary endpoint concluded if p-value will be lower than 0.05 one-sided.

In case of missing assessment of the primary endpoint, primary analyses will be performed adopting a reference-based Multiple Imputation approach (Copy Reference) to consider a missing not at random mechanism for missing data: imputation of values in the ladarixin arm will be done as if the subject had been a member of the placebo arm. This approach does not assume benefits for ladarixin in case of discontinuation and limits a post-discontinuation clinical effect to that of placebo.

Sensitivity analyses will be defined in the SAP to assess the robustness of results on primary endpoints versus the assumptions on the mechanism of missingness (missing non at random vs missing at random).

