### 7.2 Analysis of secondary efficacy endpoints

# PPD

All secondary endpoints will be analysed at each available time point by means of descriptive statistics as detailed in sections 7.2.1.1-7.2.1.10.

The following results will be displayed graphically:

- The proportion at each time point by treatment of patients with HbA1c <7% and daily insulin requirement <0.5 (IU/kg/day);
- The means ( $\pm$ SEs) at each time point by treatment of the HbA1c and its change from baseline;
- The proportion at each time point by treatment of patients with HbA1c of less than 7% who did not experience severe hypoglycemic events during treatment;
- The means ( $\pm$ SEs) at each time point by treatment of the daily insulin requirement (IU/kg/day);
- The means ( $\pm$ SEs) at each time point by treatment of the 2-hour AUC of C-peptide post MMTT and its change from baseline;
- The means ( $\pm$ SEs) at each time point by treatment of the TIR by CGM and its change from baseline.

In each graph, where possible, significant p-values from the below analyses will be reported in the plot area, in correspondence of the associated time point.

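### SAP 4.1 applies its significance threshold to a rounded p-value, which moves the cut-off from 0.05 to 0.0505, against its own alpha and Protocol 9.5.2.1; the effect is small and concerns labelling

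*SAP*

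**What the plan says.** **SAP 4.1 (General)** contains three statements that do not fit together. The level: "hypothesis testing will be carried out at the alpha = 0.050 level (one-sided) when comparing treatments". The rounding: "p-value will be rounded to three decimal places". The decision rule: "Statistical significance will be declared if the rounded one-sided p-value will be less than or equal to 0.050".

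**Protocol 9.5** gives the general level without any rounding ("the significance level used for statistical testing will be 0.05 and one-sided tests will be used"). **Protocol 9.5.2.1** states the primary decision strictly: "superiority of ladarixin in terms of primary endpoint concluded if p-value will be lower than 0.05 one-sided". **Protocol 9.1** sizes the trial on the same level: "considering a randomization ratio 2:1 (ladarixin:placebo) and a one-sided alpha of 0.05".

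**SAP 4.8** lists what changed after enrolment was stopped. Formal testing is dropped, everything becomes descriptive, and a chi-square test replaces the logistic regression and imputation. A change of threshold is not on the list.

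**SAP 7.1 and 7.2** keep between-arm tests for the primary and secondary endpoints. For the binary endpoints the test is chi-square, or Fisher's exact test where more appropriate. SAP 7.2 also carries the label into the figures: "significant p-values from the below analyses will be reported in the plot area".

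**The concern.** Rounding is a display convention. Here it is applied before the comparison with alpha, so it moves the threshold, and only towards declaring significance. Any p-value from 0.0500 to just under 0.0505 is labelled significant although it does not meet the strict limit in the protocol, nor the 0.050 level in the same SAP section (apart from exact equality).

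For a continuous p-value the band is very narrow. For a 2x2 table the p-value is discrete. One or two fairly likely tables can fall in the band, and the level then moves by more than the nominal 0.05 points. At stake is whether a borderline result carries a significance label in the report and on the graphs.

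**Working it through.** **1. The cut-off.** A p-value rounded to three decimals is at most 0.050 exactly when the unrounded value is below 0.0505. On the normal scale the critical value falls from 1.6449 to 1.6400.

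**2. Continuous p-values (t-test).** Under the null, Pr(p < c) = c. With c = 0.05 this gives the plan's stated 5.00%. With c = 0.0505 it gives 5.05%.

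**3. Chi-square: method and assumptions.** The SAP does not say how a one-sided p is taken from the chi-square. I assume the upper normal tail of z = (x/n₁ − y/n₂) / √[p̄(1 − p̄)(1/n₁ + 1/n₂)], where p̄ is the pooled proportion, without continuity correction. All tables are enumerated. The level is the sum of binomial probabilities of the rejected tables at a common response rate π. I use π = 45%, the lower end of the placebo range in Protocol 9.1.

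**4. Planned 2:1 split of 75, i.e. 50:25.** One table lies in the band, 26/50 vs 8/25:
- p̄ = 34/75 = 0.4533
- standard error = √(0.4533 × 0.5467 × 0.06) = 0.1219
- z = (0.52 − 0.32)/0.1219 = 1.640, p = 0.05049, displayed as 0.050
- smallest expected count = 34 × 25/75 = 11.3, so chi-square would normally be used
- at π = 45% this table has probability 0.48%, so the level goes from 4.88% to 5.36%
- at π = 50% it goes from 4.80% to 5.15%; at π = 55%, from 5.11% to 5.23%

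**5. 48:25 (an assumed near-planned split).** Three tables lie in the band: 23/48 vs 7/25 (p = 0.05037), 27/48 vs 9/25 (p = 0.05027) and 42/48 vs 18/25 (p = 0.05023). At π = 45% the first two have probabilities of 0.40% and 0.37%; the third is negligible. The level goes from 4.70% to 5.47%.

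**6. Small splits (assumed, because the final N is not given).**

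| Split, π | Band tables | Smallest expected count | Chi-square only: strict → rounded | Fisher if any expected count < 5: strict → rounded |
|---|---|---|---|---|
| 18:9, 50% | 12/18 vs 3/9; 10/18 vs 2/9 (both p = 0.05017) | 4.0 | 4.40% → 6.74% | 2.0% → 2.0% |
| 21:11, 56% | 14/21 vs 4/11 (p = 0.05038) | 4.8 | 4.62% → 5.77% | 2.85% → 3.07% |
| 24:12, 50% | none | n/a | 6.3% → 6.3% | not needed here |

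The one-sided Fisher p-values of the two 18:9 tables are 0.109 and 0.108. For 14/21 vs 4/11 it is 0.103. All are well outside the band.

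**7. How often it matters.** Of 115 arm-size pairs near 2:1 (placebo 4 to 26), 32 have at least one chi-square table in the band. With Fisher used whenever an expected count is below 5, this falls to 22.

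**8. What strict p < 0.05 delivers.** The uncorrected chi-square can exceed 5% without any rounding: 5.11% at 50:25 with π = 55%, 6.5% at 50:25 with π = 94%, and 6.3% at 24:12 with π = 50%. Fisher's unconditional level stays at or below 3.6% under either rule over the sizes examined (total N up to 85).

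**The case against.** The best reply is that no 5% guarantee remains to protect. SAP version 3.0 withdraws the estimand, drops formal testing, and treats all efficacy analyses as descriptive with no multiplicity correction. Against ten secondary endpoints at several visits, a shift of 0.05 points in one nominal threshold is trivial. The rule is also written down in advance and is transparent. This largely stands, and it limits the point to labelling. It does not remove it, because the same version keeps the declaration in 4.1 and the flags in 7.2.

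Three stronger readings are tempting, and the documents do not support them.

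- A reader might infer that the same Month 12 data would be significant under the SAP and not under the protocol. The protocol rule belongs to a logistic regression with Copy Reference imputation, which SAP 4.8 replaced. That analysis would give a different p-value. The thresholds conflict, but they no longer apply to the same test.
- A reader might take the 18:9 figure (4.4% to 6.7%) as the expected damage. It requires chi-square where the smallest expected count is 4.0. The SAP leaves the Fisher trigger undefined; under the usual rule of expected counts below 5, the effect at 18:9 is nil.
- A reader might infer that rounding is what pushes the chi-square above 5%. Step 8 shows that it can exceed 5% without rounding.

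The reach on the graphs is also limited. Of the six displays in SAP 7.2, two show proportions. The other four show continuous variables, for which the t-test shift is 5.00% to 5.05%.

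**Conclusion.** The inconsistency is real. SAP 4.1 conflicts with its own alpha and with the strict limit in Protocol 9.5.2.1, and SAP 4.8 does not declare the difference. Its size is 0.05 percentage points for continuous p-values. For the chi-square at 50:25 and 48:25 with a 45% common rate it is about 0.5 to 0.8 points. These figures assume an uncorrected one-sided chi-square and group sizes near the plan, which a trial with stopped enrolment may not have reached. At other sizes the effect may be larger, smaller or absent, depending on the split and on when Fisher's test is chosen.

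This is not a breach of a confirmatory error rate. The consequence is that a borderline p-value may carry a significance label that the stated 0.05 level does not support.

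**What to change.** Choose one of two changes.

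1. In SAP 4.1, state that p-values are rounded to three decimals for display only, and that any significance label uses the unrounded one-sided p-value with p < 0.05. Apply the same condition to the flags on the SAP 7.2 graphs.
2. In line with SAP 4.8 and 7, delete the significance declaration in 4.1 and the flags in 7.2, and report all p-values as nominal. This also removes the tension between significance language and a descriptive plan.

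Either way the cost is about one sentence in the SAP and one condition in the table and figure programs. The downside is that a borderline result may lose its flag. Neither change makes the uncorrected chi-square hold 5%; the first only removes the contribution of rounding and the conflict between the documents.
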